## 4 INTERIM ANALYSES

An interim analysis will be performed when approximately 50% of potentially projected available subjects have been enrolled into the study to provide information to assist the interpretation and design of ongoing clinical development of CNS remyelinating therapies.

The interim analyses will only include the following specified analyses:

- Demography as described in Section 3.2.4 including age, age category, sex and race category
- Analysis of latency as determined by FF-VEP as described in Section 3.3.2
- Analysis of time to diagnosis of CDMS as described in Section 3.3.3
- Descriptive statistics of EDSS, T25FW, 9HPT (dominant/non-dominant), PASAT 3 and SDMT
- [REDACTED]
- [REDACTED]
- Correlation analysis between new assessments at Day 1 (EDSS, T25FW, 9HPT (dominant/non-dominant), PASAT 3, SDMT, [REDACTED]) and clinical and electrophysiological recovery from baseline (FF-VEP, [REDACTED]) at Day 1.

## 5 SAMPLE SIZE DETERMINATION

The sample size is based on the number of subjects who participated in Study 215ON201 (approximately 82) rather than statistical considerations. The subjects eligible for this study must have participated in Study 215ON201.

[figure not shown]

**8 APPENDIX 2: MULTIPLE SCLEROSIS FUNCTIONAL COMPOSITE (MSFC)[1]**

There are 3 components in the MSFC (Fischer et al., 2001):

(1) The average time from the 4 trials on the 9-hole peg test (HPT) (the 2 trials for each hand are averaged, converted to the reciprocals of the mean times for each hand and then the 2 reciprocals are averaged);

(2) The average time of the 2 trials in Timed 25-Foot Walk;

(3) The number of correct answers on the Paced Auditory Serial Addition (PASAT) 3 test.

The MSFC Z-score is calculated by creating Z-scores for each component of the MSFC, as explained below, and averaging them to create an overall composite score, i.e.,

MSFC Z-score =  $(Z_{25\text{-foot-walk}} + Z_{9\text{HPT}} + Z_{\text{PASAT-3}})/3$ , where  $Z_j$  refers to Z-scores of component j.

A Z-score represents the number of standard deviations a subject’s test result is higher ( $Z > 0$ ) or lower ( $Z < 0$ ) than the average test result ( $Z = 0$ ) from the reference population. For this study, the reference population will be the subjects from Biogen 999MS005 MS COG norm healthy volunteer study, and the overall scores are given in Table 3.

**Table 3: The overall scores of T25FW, 9HPT and PASAT 3 from Biogen 999MS005 MS COG study**

	T25FW	1/9HPT	PASAT-3
mean	4.2	0.052	45.6
SD	0.95	0.0057	11.05

The Z-score for each component is defined as below:

Timed 25-Foot Walk Z-score Calculation

The Z-score is calculated as in the following formula:

$$Z_{25\text{-foot-walk}} = (-1) \times \frac{((t_1 + t_2) / 2) - MEAN(reference)}{SD(reference)},$$

where  $t_1$  and  $t_2$  are the time (in seconds) from the two trials, and the MEAN (reference) and SD (reference) are the mean and standard deviation of the averaged time from two trials for the reference population.

If a subject is missing only one trial due to reasons other than MS related physical limitation, then the time from the non-missing trial will be used to calculate the Z-score. If both trials are missing due to reasons other than MS related physical limitation then the Z-score is regarded as missing.

If either trial is missing due to MS related physical limitation, then the subject will be given a Z-score -13.7 for T25FW.

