### **EDSS, MSFC and SDMT**

For Expanded Disability Status Scale (EDSS), and its 7 functional system scores including Visual (Converted), Brainstem, Pyramidal, Cerebellar, Sensory, Bowel and Bladder (Converted), and Cerebral, each functional system score and EDSS total score will be summarized using descriptive statistics by treatment group.

For multiple sclerosis functional composite (MSFC), MSFC z-score [1] for T25FW, 9HPT and PASAT-3 will be derived as in Appendix 2 and will be summarized using descriptive statistics by treatment group.

The MSFC Z-score is calculated by creating Z-scores for each component of the MSFC, as explained below, and averaging them to create an overall composite score, i.e.,

MSFC Z-score = (Z25-foot-walk + Z9HPT + ZPASAT-3)/3, where Zj refers to Z-scores of component j.

A Z-score represents the number of standard deviations a subject's test result is higher (Z >0) or lower (Z <0) than the average test result (Z = 0) from the reference population. For this study, the reference population will be the subjects from Biogen 999MS005 MS COG norm healthy volunteer study.

For T25FW, 9HPT dominant hand, 9HPT non-dominant hand and PASAT-3, actual assessments as continuous variables will also be summarized using descriptive statistics by treatment group.

For Symbol Digit Mobility Test (SDMT), the SDMT scores will be summarized using descriptive statistics by treatment group .

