#### 9HPT Z-score Calculation

Z-score for the 9HPT is calculated as in the following formula:

$$Z_{9HPT} = \frac{\left( \left( \frac{1}{(t_{11} + t_{12}) / 2} + \frac{1}{(t_{21} + t_{22}) / 2} \right) / 2 \right) - MEAN(reference)}{SD(reference)},$$

where  $t_{11}$ ,  $t_{12}$ ,  $t_{21}$ ,  $t_{22}$  are the time (in seconds) taken to complete for dominant hand trial 1, dominant hand trial 2, non-dominant hand trial 1, and non-dominant hand trial 2, respectively. The MEAN (reference) and SD (reference) are the mean and standard deviation of averaged reciprocals of time from two hands for the reference population.

If one trial of either hand is missing due to reasons other than MS related physical limitation, then the time from the non-missing trial will be used to calculate the Z-score. If both trials of one hand are missing due to reasons other than MS related physical limitation, then the time from this hand is set as missing, and the non-missing hand will be used to calculate the Z-score. For example, if only one trial is performed per hand, then the Z-score is calculated as an average of the reciprocals of the two times; if both trials of the non-dominant hand are missing, then the Z-score is calculated based on the reciprocal of the mean time from the dominant hand.

If either trial from one hand is missing due to MS related physical limitation, then 777 seconds are assigned to the disabled hand, and Z-score is calculated using the average of the inverse of each hand.

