#### PASAT-3 Z-score Calculation

For the PASAT-3, the z-score for each subject will be calculated by subtracting the reference population's mean score from the subject's PASAT-3 score and dividing by the SD of the reference population, i.e.

$$Z_{\text{PASAT-3}} = \frac{\text{PASAT3 raw score} - \text{MEAN}(\text{reference})}{\text{SD}(\text{reference})}.$$

If a subject is missing the PASAT-3 score due to MS disease limitations, the subject will be given a Z-score calculated using a raw score of 0. If missing score is due to other reasons, then the Z-score is regarded as missing.

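### The fixed T25FW score for MS-related inability (Z = -13.7) equals only 17.2 s on the SAP's own reference, so a slower walker who finishes scores worse than a subject who cannot

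*SAP*

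**What the plan says.** SAP Appendix 2 scores a walker by averaging the two trial times, subtracting the reference mean, dividing by the reference SD and reversing the sign, so lower Z means worse. The reference is a healthy-volunteer study. Table 3 reads "mean 4.2 0.052 45.6" and "SD 0.95 0.0057 11.05", with T25FW in the first column, 1/9HPT in the second and PASAT-3 in the third.

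Appendix 2 treats a missing walk according to its reason:

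- MS prevented a trial: "If either trial is missing due to MS related physical limitation, then the subject will be given a Z-score -13.7 for T25FW".
- One trial is missing for another reason ("If a subject is missing only one trial due to reasons other than MS related physical limitation"): the remaining time is used in the formula.
- Both trials are missing for other reasons: Z is missing.

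For the other two components, inability is entered as a raw value and then standardised on Table 3. For 9HPT, "then 777 seconds are assigned to the disabled hand"; for PASAT-3, "the subject will be given a Z-score calculated using a raw score of 0".

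No T25FW time limit, cap or floor on Z is stated in Appendix 2, in SAP Section 3.3.3 or in the protocol text available. SAP Section 3.3.3 averages the three component Z-scores into the MSFC Z-score. It adds that for T25FW, each hand of the 9HPT and PASAT-3, "actual assessments as continuous variables will also be summarized using descriptive statistics by treatment group".

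**The concern.** A Z-score has meaning only relative to the mean and SD used to form it. The value -13.7 is written as a constant, with no time behind it and no stated link to Table 3, while completers are scored on Table 3 without limit. If the constant lies inside the range that completers can reach, the scale stops being ordered: being unable to walk 25 feet can score better than walking it slowly.

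The T25FW Z is one third of the MSFC Z-score, a named secondary measure of disease severity, so any inversion passes into the composite. SAP Section 3.1 plans means and SDs by treatment group as well as medians and ranges. Because Z has no lower bound, one very slow completer can pull an arm mean.

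**Working it through.** **Inputs.** Inability score -13.7, T25FW mean 4.2 s and SD 0.95 s, 1/9HPT mean 0.052 and SD 0.0057, PASAT-3 mean 45.6 and SD 11.05 (all SAP Appendix 2). Maximum 41 per arm (protocol Section 5.5.2). A figure of 25 per arm is an assumption for illustration. The SAP gives no derivation of -13.7, so the constant cannot be reproduced, only converted to a time.

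**Step 1: the time equivalent to -13.7.** From Z = -(t - 4.2)/0.95,

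t = 4.2 + 13.7 × 0.95 = 17.215 s.

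Allowing for rounding of all three figures, the range is 4.15 + 13.65 × 0.945 = 17.05 s to 4.25 + 13.75 × 0.955 = 17.38 s.

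**Step 2: completers against an unable subject.** The composite difference is (Z + 13.7)/3, with 9HPT and PASAT-3 held equal.

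| Average time (s) | T25FW Z | Composite difference |
|---|---|---|
| 15 | -11.37 | +0.78 |
| 18 | -14.53 | -0.28 |
| 20 | -16.63 | -0.98 |
| 25 | -21.89 | -2.73 |
| 30 | -27.16 | -4.49 |

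The order is right at 15 s and wrong at every time above 17.215 s.

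**Step 3: one subject under the different rules.** Suppose the first trial takes 25 s.

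- Second trial also 25 s: Z = -21.89.
- Second trial missing for a non-MS reason: Z = -21.89.
- Second trial prevented by MS: Z = -13.7.

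On the same observed walk, inability raises Z by 21.89 - 13.7 = 8.19, or 2.73 on the composite.

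**Step 4: effect on an arm mean.** Replace one unable subject by one completer and divide the composite difference by the arm size:

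- 20 s: 0.977/25 = 0.039; 0.977/41 = 0.024.
- 30 s: 4.486/25 = 0.179; 4.486/41 = 0.109.

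**Step 5: the other two components.**

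- 9HPT, both hands at 777 s: (1/777 - 0.052)/0.0057 = -8.897. As time grows without limit, Z tends to -0.052/0.0057 = -9.123. A completer at 300 s with both hands scores -8.54, still better than inability. The order can reverse only beyond 777 s, and by at most 9.123 - 8.897 = 0.226.
- PASAT-3 raw score 0: -45.6/11.05 = -4.13. No lower raw score exists, so the order cannot reverse.

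Only the T25FW rule gives an inversion that is unbounded and begins at a modest time.

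**The case against.** The best counter-argument accepts the arithmetic and disputes its weight.

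- **Consequences are few.** MSFC is summarised descriptively, the raw walk times are tabulated separately, and medians and ranges are planned. The visible interim list in SAP Section 4 names the component tests but not the composite. No primary result or decision rule depends on the MSFC Z-score. This stands.
- **The cases are hypothetical.** The documents report no walk times for this cohort, and the parent study enrolled subjects with a first optic neuritis episode. An actual misordering needs both a completer above 17.2 s and a subject unable because of MS, among at most 82. This also stands. At 20 s the change in arm mean is only 0.02 to 0.04.
- **The missing-trial rules do not contradict each other.** They depend on the reason for missingness, so no subject falls under both. That is correct. The 25 s example is the same inversion seen within one subject, not a second fault.
- **9HPT also has no cap.** True, but the possible reversal there is at most 0.226 and needs times above 777 s.
- **The constant or a time limit may come from the MSFC scoring manual that the SAP cites.** This cannot be checked from the documents. It would not rescue the rule: the inversion on Table 3 remains unless a time limit of about 17.2 s or less applies, and none is stated.

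These points limit the impact. None restores the ordering.

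**Conclusion.** The concern holds. As written, the T25FW rule ranks inability above any completed walk averaging more than 17.215 s (17.05 to 17.38 s allowing for rounding). The composite penalty for a completer relative to an unable subject is 0.98 at 20 s and 4.49 at 30 s. One such subject in place of an unable one moves an arm-mean MSFC by 0.02 to 0.04 at 20 s, and by 0.11 to 0.18 at 30 s, for 41 and an assumed 25 per arm.

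This rests on the Table 3 reference being the one used and on no time limit of about 17.2 s or less applying to the test. The FF-VEP primary endpoint and the raw T25FW summaries are unaffected. Expected impact is limited, and nil if no completed average exceeds 17.2 s. Even so, this is a scoring rule that can give the wrong order in a named secondary measure, not merely a missing detail, and it should be corrected.

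**What to change.** In SAP Appendix 2, state that any T25FW Z below the inability score is set equal to the inability score, so that inability never scores better than a completed walk. There are two ways to do this:

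1. Keep -13.7 and use it as the common floor.
2. State a maximum time T, set the inability score to -(T - 4.2)/0.95, and cap completed times at T. The documents give no T, so the sponsor would have to specify and justify one.

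In either case, give the source of the constant. Settle this before walk times are examined by treatment group, since a floor chosen afterwards would be post hoc.

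The cost is one or two sentences and one line of code, with no new data. The downside is that the slowest completers tie with those unable, and measured differences among them are lost from Z, though they remain in the raw-time summaries. Under the first option the tie begins at 17.2 s. With a longer T it begins later, but each unable subject then pulls the arm mean further.

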#### 9HPT Z-score Calculation

Z-score for the 9HPT is calculated as in the following formula:

$$Z_{9HPT} = \frac{\left( \left( \frac{1}{(t_{11} + t_{12}) / 2} + \frac{1}{(t_{21} + t_{22}) / 2} \right) / 2 \right) - MEAN(reference)}{SD(reference)},$$

where  $t_{11}$ ,  $t_{12}$ ,  $t_{21}$ ,  $t_{22}$  are the time (in seconds) taken to complete for dominant hand trial 1, dominant hand trial 2, non-dominant hand trial 1, and non-dominant hand trial 2, respectively. The MEAN (reference) and SD (reference) are the mean and standard deviation of averaged reciprocals of time from two hands for the reference population.

If one trial of either hand is missing due to reasons other than MS related physical limitation, then the time from the non-missing trial will be used to calculate the Z-score. If both trials of one hand are missing due to reasons other than MS related physical limitation, then the time from this hand is set as missing, and the non-missing hand will be used to calculate the Z-score. For example, if only one trial is performed per hand, then the Z-score is calculated as an average of the reciprocals of the two times; if both trials of the non-dominant hand are missing, then the Z-score is calculated based on the reciprocal of the mean time from the dominant hand.

If either trial from one hand is missing due to MS related physical limitation, then 777 seconds are assigned to the disabled hand, and Z-score is calculated using the average of the inverse of each hand.

#### PASAT-3 Z-score Calculation

For the PASAT-3, the z-score for each subject will be calculated by subtracting the reference population's mean score from the subject's PASAT-3 score and dividing by the SD of the reference population, i.e.

$$Z_{\text{PASAT-3}} = \frac{\text{PASAT3 raw score} - \text{MEAN}(\text{reference})}{\text{SD}(\text{reference})}.$$

If a subject is missing the PASAT-3 score due to MS disease limitations, the subject will be given a Z-score calculated using a raw score of 0. If missing score is due to other reasons, then the Z-score is regarded as missing.
